## **5.5 Early Termination of Study Visits**

If the subject has not undergone relevant assessments and examinations within 7 days prior to withdrawal, the following should be performed:

- ✓ ECOG score;
- ✓ Vital signs: Pulse, respiratory rate, body temperature, blood pressure;
- ✓ Comprehensive physical examination: General condition, head and face, skin, lymph nodes, neck, eyes, ENT, oral cavity, respiratory system, cardiovascular system, abdomen, reproductive-urinary system, musculoskeletal system, nervous system, mental status, and others;
- ✓ Blood routine: Red blood cell count, hemoglobin, platelet count, white blood cell count, neutrophil count, lymphocyte count;
- ✓ Urinalysis: White blood cell count, red blood cell count, urine protein. If urine protein is  $\geq 2+$ , a 24-hour urine protein test is required;
- ✓ Clinical chemistry: ALT, AST, GGT, total bilirubin, direct bilirubin, AKP, blood urea nitrogen or urea (blood urea nitrogen is preferred), total protein, albumin, creatinine, blood glucose, lactate dehydrogenase, K+, Na+, Ca2+, Mg2+, Cl;

- ✓ Thyroid function: TSH, FT3, FT4;
- ✓ EBV-DNA test;
- ✓ ECG;
- ✓ Radiological examination: Subjects who withdraw from the study should undergo a radiological examination at the end of treatment or at the time of withdrawal if no such examination has been performed within 3 weeks before withdrawal. In addition to radiologically confirmed PD, subjects who discontinue study treatment for other reasons should also undergo radiological examination every 6 weeks until documented PD, initiation of new antitumor therapy or death.
- ✓ AEs: AEs should be recorded in detail;
- ✓ Concomitant medication: Concomitant medication should be recorded in detail.

## **5.6 Unscheduled Visits**

During the study, if unscheduled follow-up is required due to AE occurring within 90 days after the last dose or within 90 days before a new antitumor therapy, the following should be recorded:

- ✓ Concomitant medications;
- ✓ Adverse events;
- ✓ All relevant examinations performed (including radiological examination, if any).

## **6. EFFICACY EVALUATION**

### **6.1 Efficacy Evaluation Criteria**

Efficacy is evaluated according to the European Response Evaluation Criteria in Solid Tumors (RECIST 1.1) (see Attached Appendix II).

## **6.2 Efficacy Endpoints and Definitions**

### **6.2.1 Efficacy endpoints**

Efficacy endpoints mainly include disease control rate (DCR), progression free survival (PFS), overall survival (OS), overall response rate (ORR) and duration of response (DOR).

### **6.2.2 Definition of endpoints**

Disease control rate (DCR) is defined as the percent of subjects with complete response (CR), partial response (PR) or stable disease (SD) as the best overall response;

Overall response rate (ORR) is defined as the percent of subjects with CR or PR as the BOR;

Progression free survival (PFS) is defined as the time from enrollment to PD or death due to any cause. For subjects with unknown disease status, PFS refers to the time from enrollment to last the follow-up;

Overall survival (OS) is defined as the time from enrollment to death due to any cause. If it is unclear whether the subject has died, OS refers to the time from enrollment to the last follow-up;

Complete remission (CR) is defined as the percent of subjects with CR as BOR.

Partial remission (PR) is defined as the percent of subjects with PR as BOR.

Duration of response (DOR) is defined as the time from the first documented response (CR or PR) to progressive disease (PD) or recurrence.

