## **5.3 Treatment Period**

- The following assessments should be completed before each dose in each cycle. If the test is completed within 7 days before the first dose during the screening

period, it is not required prior to the first dose.

- ✓ ECOG score;
- ✓ Vital signs: Pulse, respiratory rate, body temperature, blood pressure;
- ✓ Physical examination: General conditions, head and face, skin, lymph nodes, neck, eyes, ENT, oral cavity, respiratory system, cardiovascular system, abdomen, reproductive-urinary system, musculoskeletal system, nervous system, mental status, and others;
- ✓ Blood routine: Complete blood count and differential count (white blood cells, red blood cells, lymphocytes, monocytes, neutrophils, basophils, eosinophils, hemoglobin), platelet count;
- ✓ Clinical chemistry: ALT, AST, GGT, total bilirubin, direct bilirubin, AKP, blood urea nitrogen or urea (blood urea nitrogen is preferred), total protein, albumin, creatinine, blood glucose, lactate dehydrogenase, K+, Na+, Ca2+, Mg2+, Cl;
- ✓ EBV-DNA test;
- ✓ Urinalysis: White blood cell count, red blood cell count, urine protein. If urine protein is  $\geq 2+$ , a 24-hour urine protein test is required;
- ✓ Routine stool test: White blood cells, red blood cells, occult blood;
- ✓ Coagulation function: Prothrombin time, activated partial thromboplastin time, thrombin time, fibrinogen, D-dimer, international normalized ratio;
- ✓ Thyroid function: TSH, FT3, FT4 (FT3 and FT4 can be replaced by T3 and T4 if they are not available);
- ✓ 12-lead electrocardiogram (12-Lead ECG): Additional necessary tests should be performed according to the judgment of the investigators in case of any abnormality;
- ✓ Concomitant medication: Concomitant medication should be recorded in detail;
- ✓ AEs: AEs should be recorded in detail;
- Radiological examination (completed before dosing every two cycles): CT or MRI of the nasopharynx, neck, chest, and abdomen (including the pelvis). An enhanced scan is preferred if not contraindicated. The radiological examination should be performed every 6 weeks. For bone metastases, a bone scan is

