performed only if the response for other lesions is assessed as CR and it is necessary to confirm whether bone metastases have completely disappeared or there are clinical indications. Subjects who withdraw from the study for any reason should undergo radiological examination at the time of withdrawal if no such examination has been performed within 3 weeks. Conditions for radiological examination should be the same as those at baseline (including scan slice thickness and contrast agent). A time window of  $\pm 7$  days is permitted for radiological examination, and unscheduled radiological examination can be performed when PD is suspected (e.g., symptomatic deterioration). In addition to radiologically confirmed PD, subjects who discontinue study treatment for other reasons should also undergo radiological examination every 6 weeks until documented PD, initiation of new antitumor therapy, loss to follow-up, or death. The time of radiological examination will not be adjusted for the delayed dosing period.

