## **5.4 Follow-up**

On-site follow-ups will be conducted 30 days after the last dose at the study site, and safety information (including AE outcome, new SAEs, and adverse events of special interest) will be collected by telephone follow-ups at 60 and 90 days after the last dose, with a time window of  $\pm 7$  days.

If a subject starts a new antitumor therapy within 30 days after the last dose, the follow-up should be completed before the new antitumor therapy.

- ✓ Blood routine: Red blood cell count, hemoglobin, platelet count, white blood cell count, neutrophil count, lymphocyte count;
- ✓ Clinical chemistry: ALT, AST, GGT, total bilirubin, direct bilirubin, AKP, blood urea nitrogen or urea (blood urea nitrogen is preferred), total protein, albumin, creatinine, blood glucose, lactate dehydrogenase, K+, Na+, Ca2+, Mg2+, Cl;
- ✓ Thyroid function: TSH, FT3, FT4;
- ✓ AEs: AEs should be recorded in detail;

Concomitant medication: Concomitant medications are recorded until 90 days after the last dose. Concomitant medications for study drug-related AEs are recorded until 30 days after the last dose.

Survival follow-up will be performed by telephone and other effective methods once a month from the last dose to determine if the subject has initiated new antitumor therapy subsequently. If so, the treatment regimen, as well as start and end time will be recorded and the survival follow-up form will be completed.

For subjects who withdraw from the study due to "non-PD" (such as intolerable AEs), tumor assessment is recommended to be performed according to the frequency of efficacy evaluation specified in this study (every 6 weeks  $\pm$  7 days) during the tumor progression follow-up until PD, death or initiation of new antitumor therapy. The follow-up information should be recorded in the CRF.

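### PFS for patients of unknown disease status ends at last follow-up, not at the last tumour assessment, so unscanned time can count as progression-free

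*Protocol*

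**What the plan says.** **PFS.** Section 6.2.2 gives the event: "Progression free survival (PFS) is defined as the time from enrollment to PD or death due to any cause". For patients whose status is not known it adds: "For subjects with unknown disease status, PFS refers to the time from enrollment to last the follow-up".

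**OS.** The next definition has the same end point: "If it is unclear whether the subject has died, OS refers to the time from enrollment to the last follow-up".

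**Imaging.** Section 5.3: "The radiological examination should be performed every 6 weeks", with a window of 7 days either way. For patients who stop treatment for reasons other than radiological PD, scans go on "until documented PD, initiation of new antitumor therapy, loss to follow-up, or death". Section 5.5 says much the same. Section 5.4 is softer for these patients: "tumor assessment is recommended to be performed according to the frequency of efficacy evaluation specified in this study".

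**Contact without imaging.** Section 5.4: "Survival follow-up will be performed by telephone and other effective methods once a month from the last dose". These contacts also record whether a new antitumour therapy has begun.

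**DOR.** Section 6.2.2: "Duration of response (DOR) is defined as the time from the first documented response (CR or PR) to progressive disease (PD) or recurrence".

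**Analysis.** Section 9.3.3 plans Kaplan-Meier curves and medians for PFS, OS and DOR. Section 2.3 makes DCR primary and PFS and DOR secondary.

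**The concern.** Vital status is known at the last contact, but RECIST status is known only at the last scan. A rule that ends PFS at last follow-up treats the two as the same.

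The trial can be expected to produce patients for whom they differ:
- a patient who stops for toxicity and starts another drug is no longer scanned but is still telephoned every month;
- a patient withdrawn without PD may stop being scanned, because section 5.4 only recommends it;
- section 3.5.2 allows withdrawal for clinical progression judged by the investigator, while Appendix II (2.7) says symptomatic deterioration is not an objective response, so such a patient may have no documented PD.

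Read literally, the rule keeps these patients in the risk set as progression-free until death or last contact. Survival on a later therapy is then credited to PFS on anlotinib. A single-arm trial has no comparator carrying the same bias, so readers will set the PFS against published values for other treatments.

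**Working it through.** The protocol states no expected PFS, so there is no figure of its own to reproduce. The check asks which way the rule moves the curve, and by how much over a plausible range.

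**Inputs from the protocol:** PFS event is PD or death; scans every 6 weeks; monthly contact after the last dose; Kaplan-Meier estimation; 39 patients.

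**Assumptions, not in the protocol:** exponential times; true median PFS *m* of 3 to 6 months; median time from progression to death *p* of 6 to 8 months; a share *f* of 10, 20 or 30% leaving imaging before PD (about 4, 8 or 12 of 39 patients), unrelated to prognosis; contact continuing to death.

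**Formulas (continuous time).** Let λ = ln 2/*m*, δ = ln 2/*p*, and σ = λ*f*/(1 − *f*), the rate of leaving imaging.

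- Censored at last assessment: S_A(t) = exp(−λt).
- As written: S_B(t) = exp(−λt) + λ·exp(−δt)·[(1 − exp(−(λ−δ)t))/(λ−δ) − (1 − exp(−(λ+σ−δ)t))/(λ+σ−δ)].

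The added term is the share of patients who left imaging, have since progressed unseen, and are still alive. It cannot be negative, so the bias under these assumptions is always upward.

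**Worked case:** *m* = 3, *p* = 6, *f* = 0.10, t = 6 months. λ = 0.2310, δ = 0.1155, σ = 0.0257. S_A = 0.250. Added term = 0.1155 × (4.328 − 4.047) = 0.0325. S_B = 0.282. A simulation of 400,000 patients also gave 0.282; with contact for only 3 months after leaving it gave 0.272.

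**Results, with *f* = 10 / 20 / 30%:**

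| *m* / *p* (months) | Median as written (months) | 12-month PFS, last assessment | 12-month PFS, as written |
|---|---|---|---|
| 3 / 6 | 3.1 / 3.3 / 3.6 | 6.3% | 10.4 / 14.6 / 18.9% |
| 4 / 8 | 4.2 / 4.4 / 4.8 | 12.5% | 16.6 / 21.0 / 25.7% |
| 5 / 7 | 5.2 / 5.5 / 6.0 | 18.9% | 22.2 / 25.7 / 29.6% |
| 6 / 8 | 6.3 / 6.6 / 7.1 | 25.0% | 27.9 / 31.1 / 34.7% |

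The median rises by about 4 to 5% at *f* = 10%, 10 to 11% at 20%, and 19 to 21% at 30%. Twelve-month PFS rises by about 3 to 4 points at 10%, and by 6 to 13 points at 20 to 30%.

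**On a 6-weekly scan grid** (*p* = 8 months, data cut at 12 to 36 months), simulated 12-month PFS at last assessment against as written was:
- true median 4 months, 12% leaving: 14.8% against 19.1%;
- true median 4 months, 23% leaving: 14.7% against 23.6%;
- true median 6 months, about 22% leaving: 27.2% against 33.8%.

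The median behaves differently here. Progression is dated to scans, so the median mostly moves in steps of about 1.4 months. At a true median of 4 months the curve at the 4.14-month scan is 0.5^(4.14/4) = 48.8%, so a very small bias pushes the median to the next scan at 5.5 months. At true medians of 3 or 4.5 months, with about 20 to 25% leaving, it does not move.

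**Scale.** Ignoring censoring, the standard error of a 12-month PFS of 12.5% in 39 patients is √(0.125 × 0.875/39) = 5.3 points. The 4.1-point bias at 10% leaving is below one standard error; the 13.2-point bias at 30% is about two and a half.

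**The case against.** **The wording may mean something narrower.** The rule covers only patients of unknown status. Sections 5.3 and 5.5 keep patients who stop without PD on 6-weekly scans, and section 5.4 names a follow-up for tumour progression beside the survival follow-up. Last follow-up under PFS could mean the former. That reading is possible, but section 6.2.2 does not state it and gives OS the same end point. For a patient still being scanned, the gap is at most about one scan interval.

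**The bias is bounded.** Death remains a PFS event. A reader might infer that unscanned patients stay progression-free indefinitely; they do so only until death or last contact.

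**The planned summary is the median.** Section 9.3.3 names no 12-month rate, and the tail is where the rule bites hardest. This stands. A reader might also infer that the reported median would be overstated by a full scan interval, from 4.1 to 5.5 months. That shift depends on a true median lying just below a scan date and is not a general result.

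**The leaving rate has no source.** The nearest figure is the 10% dropout in section 3.2, which serves the sample size and is not a rate of leaving imaging. This stands too.

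**DOR.** A reader might infer that leaving death out biases DOR upward by a material amount. The documents do not support a size: the wording follows the RECIST text in Appendix II (2.8), and no DOR calculation was made. What remains is that PFS counts such a death and DOR does not.

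**Importance.** PFS and DOR are secondary and descriptive. No sample size, test or efficacy threshold depends on them.

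**Conclusion.** The point holds in a limited form. Section 6.2.2 states a rule, so this is not a detail left open for an analysis plan, and a plan that censored at the last scan would depart from it. Read as written, it biases Kaplan-Meier PFS upward.

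The direction follows from the rule; the size does not. The figures above assume exponential times, leaving unrelated to prognosis, and illustrative medians and leaving rates. With about 10% leaving imaging the effect on the planned median is small, and often nil on the scan grid. With 20 to 30% leaving it becomes large enough to affect comparison with published PFS.

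This should be fixed, but it does not threaten the trial's main conclusion: the primary DCR and its decision rule are unaffected. The DOR matter is one of consistency only.

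**What to change.** Replace the sentence on unknown disease status in section 6.2.2 with wording such as:

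*Subjects without documented PD or death are censored for PFS at the last evaluable tumour assessment (before any new antitumour therapy); last contact is used for OS only.*

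Also say whether a death after new antitumour therapy, or after scanning has stopped, counts as a PFS event. That is a choice of estimand; the comparison above does not count such deaths. Censoring at the last assessment recovers the true curve only if leaving imaging is unrelated to prognosis, so report how many patients left imaging before PD and why.

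For DOR, add one clause stating how death without documented PD is handled.

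The cost is a sentence or two. Scan, new-therapy and contact dates are already collected under sections 5.3 and 5.4. The reported PFS may be shorter.

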## **6.3 Methods of Efficacy Evaluation**

Efficacy is primarily evaluated by MRI, CT, or nasopharyngoscopy at the site of lesion. Refer to RECIST 1.1 for specific evaluation criteria.

## **7. SAFETY EVALUATION**

Safety is evaluated as per NCI CTCAE v5.0 (see Attached Appendix III) in this study. The investigator is responsible for monitoring the safety of all subjects enrolled in this study and recording any AEs and serious adverse events (SAEs).

### **7.1 Adverse Events**

AE is defined as any untoward medical occurrence in a subject administered a pharmaceutical product which does not necessarily have a causal relationship with this treatment. AE includes any unfavorable symptoms, signs and diseases temporally but is not necessarily associated with drug administration (worsening of a pre-existing condition during the study is also considered an AE). According to the GCP, the investigator should truthfully record all AEs in the original records and copy them into the case report form (CRF) regardless of their causal relationship with the study drug.

### **7.2 Serious Adverse Events**

SAE is one of the following AEs occurring under any dose of the study drug or at any time during observation:

- Death: Death within 30 days after receiving the study drug, or death after 30 days due to delayed toxicity of the study drug (except death due to PD and death unrelated to the study drug);
- Serious, life-threatening toxicity requiring hospitalization or prolonged hospitalization;
- Permanent disability or dysfunction;
- Secondary tumors;
- Congenital anomaly or birth defect;
- Other important medical events.

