## **7.4 Documentation of Events**

AEs observed during the study should be recorded in the CRF, and those observed within 30 days after the last dose should also be recorded in the CRF if they are related to the study drug. Documentation of AEs should include event description, onset and end time, severity and frequency, whether treatment is required (if yes, the treatments given should be recorded), and whether the AE is related to the study drug as judged by the investigator.

Events should be tracked until resolution. Medical documentation of AEs should be documented in source documents (including the report of test results). If the subjects discontinue treatment due to the end of the study or discharge, the investigator should send the subjects' case summary (including treatment arrangement and instructions on whether continued follow-up is required for relevant AEs) to the physician in charge of continued treatment. The above information should also be documented in the source documents.

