## **7.5 Reporting of Serious Adverse Events**

In case of any SAEs during the trial, the study site(s) should immediately take measures to ensure the safety of the subjects and report verbally to the administrative

authorities and the sponsor in a timely manner. SAEs should be reported in writing to the Department of Safety Supervision of the National Medical Products Administration, sponsor, principal investigator, the Ethics Committee and local regulatory authorities within 24 hours of their occurrence. The investigator should record the onset time, duration, measures taken and outcome of the SAE on the report, and sign and date the report.

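### The exception in the SAE death criterion (7.2) makes the SAE status of a death within 30 days depend on the investigator's attribution, and 7.4 adds a relatedness condition after the last dose

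*Protocol*

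**What the plan says.** Section 7.1 defines an adverse event as one "which does not necessarily have a causal relationship with this treatment". It tells the investigator to record every AE and to "copy them into the case report form (CRF) regardless of their causal relationship with the study drug".

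Section 7.2 presents serious events as a subset of these: "SAE is one of the following AEs occurring under any dose of the study drug or at any time during observation". The first criterion is "Death within 30 days after receiving the study drug, or death after 30 days due to delayed toxicity of the study drug". A bracket follows directly: "except death due to PD and death unrelated to the study drug". The second criterion is worded as a toxicity that is serious, life-threatening and leads to or prolongs hospitalization.

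Section 7.4 lists, among the items to document for each AE, "whether the AE is related to the study drug as judged by the investigator". It requires AEs seen during the study to be entered in the CRF, but those in the 30 days after the last dose only where they are drug-related. Section 5.4 schedules an on-site visit 30 days after the last dose, with AEs to be recorded in detail. The calls at 60 and 90 days collect, among other things, new SAEs.

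Section 7.5 requires SAEs to be reported in writing to the regulator, the sponsor, the principal investigator and the ethics committee "within 24 hours of their occurrence".

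Safety is part of the primary objective (2.1), and the synopsis names SAEs among the safety endpoints.

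**The concern.** Whether an event is serious and whether the drug caused it are normally judged separately. Here the death criterion combines them: an opinion on cause is needed before it is known whether a death is an SAE, and so before it is known whether 7.5 applies.

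That matters in this trial for three reasons. The protocol treats fatal bleeding from tumor near vital vessels as a real risk (exclusion 3.4.8) and states that anlotinib increased hemorrhage compared with placebo (4.6.1), so tumor and drug are competing explanations for a fatal bleed. The trial is open-label and single-arm, so no control group can show whether such deaths exceed what the disease alone would produce. And treatment continues until progression or intolerable toxicity (4.3), so many deaths soon after the last dose will coincide with progression, which is one of the two excepted classes.

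At stake are the prompt report of some early deaths and the completeness of the fatal SAE count. DCR, the sample size and the success rule are not touched.

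**Working it through.** No formula in the plan bears on this, and there is no stated figure to reproduce. The check is to read the sections against each other.

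**Step 1: which deaths the bracket can affect.** The death criterion has two limbs.

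- Limb A: death within 30 days, with no condition on cause.
- Limb B: death after 30 days, only if due to delayed toxicity of the drug.

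A death that satisfies limb B is by definition drug-related and not due to progression. The bracket removes nothing from limb B, so any effect it has is on limb A.

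**Step 2: outcome by case.** I take the 30 days as running from the most recent dose, because 7.2 does not name the dose. The two SAE columns give the status under the death criterion when the bracket is read as covering both limbs, and when it is read as covering limb B alone.

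| Death | SAE if bracket covers both limbs | SAE if bracket covers limb B only | AE entry required by 7.4 |
|---|---|---|---|
| On treatment, drug-related | Yes | Yes | Yes |
| On treatment, due to PD or unrelated | **No** | Yes | Yes |
| Within 30 days after last dose, drug-related | Yes | Yes | Yes |
| Within 30 days after last dose, due to PD or unrelated | **No** | Yes | **No** |
| Within 30 days, relation uncertain | Yes | Yes | Yes on treatment; unclear after last dose |
| After 30 days, delayed toxicity | Yes | Yes | Not addressed |

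Only the second and fourth rows change with the reading. These are the rows where cause decides seriousness.

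**Step 3: the fourth row.** An unrelated death in the 30 days after the last dose is not an SAE under the death criterion if the bracket covers limb A, and 7.4 does not ask for it as an AE. Section 5.4 asks for AEs in detail at the 30-day visit, and 7.1 asks for all AEs whatever the cause. The sections give different instructions for the same death. The calls at 60 and 90 days do not clearly close the gap, because for new events they ask for SAEs and events of special interest, and SAE takes its meaning from 7.2.

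**Step 4: size.** With the planned 39 patients as denominator, one death is 1/39 = 2.6%, two are 2/39 = 5.1% and three are 3/39 = 7.7%. The protocol gives no death rate. As an assumption for illustration only: with three deaths inside the window, excepting one lowers the fatal SAE proportion from 7.7% to 5.1%, and excepting two lowers it to 2.6%. With no excepted deaths it does not move.

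**The case against.** The strongest reply is grammatical. The bracket stands directly after limb B and may qualify it alone, as a clarification. Every death within 30 days would then be an SAE and no causality rule would exist. The wording does allow this. But on that reading the bracket does nothing, and a site can still apply it to early deaths. Both readings call for the same edit.

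Several stronger conclusions are tempting and are not supported:

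- **That 7.2 contradicts 7.1.** Section 7.1 governs the definition and recording of AEs, and an event can be a recorded AE without being an SAE. The tension is one of principle. The conflict in actual instructions lies between 7.4 and sections 7.1 and 5.4, for the 30 days after the last dose.
- **That excepted deaths are not counted at all.** On-treatment deaths are recorded as AEs under 7.1 and 7.4, AE incidence and outcome are described under 9.3.2, and OS in 6.2.2 counts death from any cause. What is lost is SAE status and the expedited report.
- **That a death is an SAE only when the investigator blames the drug.** The bracket excepts two classes, and a death of uncertain relation falls in neither. A fatal bleed might also qualify under another criterion, such as life-threatening toxicity or other important medical events, although the explicit exception for deaths points the other way.
- **That the death criterion is the only one in 7.2 with a causal element.** The word *toxicity* in the second criterion also implies drug causation, so rewriting the death criterion alone would leave a similar filter in place.

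It can also be said that exempting progression deaths from expedited reporting is a legitimate choice. That stands. But the bracket goes further, to any death called unrelated, and it works by removing SAE status and not by setting a reporting exemption.

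**Conclusion.** The point holds in a limited form. On the only reading that gives the bracket any effect, a death within 30 days loses SAE status under the death criterion, and with it the 24-hour written report, once the investigator attributes it to progression or judges it unrelated. For deaths after the last dose, the condition in 7.4 removes the backstop: an unrelated death may be neither an SAE nor a required AE entry under that section, while 5.4 points the other way.

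This rests on reading the bracket as more than redundant and on counting the 30 days from the most recent dose. The numerical effect is unknown. The 2.6% per death is arithmetic on the planned enrollment, and the number of excepted deaths is an assumption. The matter concerns safety reporting and does not threaten the efficacy conclusion. It is worth a short amendment because safety is in the primary objective and there is no control group against which to check attribution.

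**What to change.** - **7.2, death criterion.** Delete the bracket. Define the criterion as any death from first dose to 30 days after the last dose, whatever the cause, plus any later death considered related to the study drug.
- **7.2, second criterion.** Reconcile the word *toxicity* with the causality-free definition in 7.1.
- **7.4.** Remove the relatedness condition for deaths and SAEs in the 30 days after the last dose, and align the section with 5.4 and 7.1. Record cause of death (progression, drug, other) as a separate field.
- **7.5.** If progression deaths are to be exempt from expedited reporting, say so here and still list them in the safety tables.

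The cost is a one-line change to the death criterion, small edits to the other sections and a few more SAE reports. No endpoint, dose or sample size changes.
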